9.2.9.3. Monitoring for SARS-CoV-2 Reinfection

Patients in the long COVID sub-study will be asked to report any positive SARS-CoV-2 local test results obtained outside of the study, starting from the day at which they consent to the long COVID sub-study. Test results obtained prior to the date of consent will not be collected. Positive results will be reported as an AESI (Section 10.1.4).

Details regarding the positive SARS-CoV-2 local test result (eg, date of testing, specimen type, assay used) will be captured in the corresponding AESI data collection page.

9.2.9.4. Recording New Medical Diagnoses or Conditions

In the long COVID sub-study, any new medical condition(s) diagnosed after randomization (eg, newly diagnosed diabetes mellitus) will be captured and reported as an AESI, but will not require expedited reporting (Section 10.1.4).

Patients who previously consented to the sub-study but have already completed their end of study visit will be asked to consent to have this information collected.

Details regarding the new diagnoses or conditions (eg, preferred term [PT] for the diagnosis, date of diagnosis, and any other available information) will be captured in the corresponding AESI data collection page.

9.2.10. Pharmacogenomic Analysis (Optional)

Eligible patients who agree to participate in the genomics sub-study will be required to consent to this optional sub-study before collection of samples. When enrollment was open, newly-enrolled patients had blood samples collected for both DNA and RNA. Patients who are currently enrolled and subsequently consent to the sub-study will only have a blood collection for DNA. Patients who have already consented to this sub-study cannot consent a second time.

The blood sample for RNA must be collected pre-dose on day 1. Blood sample for DNA should be collected at the screening/baseline visit but may be collected at any visit.

The samples will be collected for pharmacogenomics analyses to understand the genetic and/or transcriptional determinants of efficacy and safety associated with the treatments in this study and the molecular basis of COVID-19 (and long COVID, as applicable). These samples will be single-coded as defined by the International Council for Harmonisation (ICH) guideline E15. Samples will be stored for up to 15 years after the final date of the database lock (or for a shorter time period if required per regional laws and regulations). If there are specific site or country requirements involving the pharmacogenomic analyses which the Sponsor is unable to comply with, samples will not be collected at those sites.

The purpose of the pharmacogenomic analyses is to identify genomic and/or transcriptional associations with clinical or biomarker response to REGN10933+REGN10987, other COVID-19 clinical outcome measures and possible treatment-emergent SAEs and AESIs. In addition, associations between genomic variants and prognosis or progression of COVID-19 (and long

COVID, as applicable). may also be studied. These data may be used or combined with data collected from other studies to identify and validate genomic and transcriptional markers related to the study drug, target pathway, COVID-19, or long COVID.

Analyses may include sequence determination or single nucleotide polymorphism studies of candidate genes and surrounding genomic regions. Other methods, including whole-exome sequencing, whole-genome sequencing, DNA copy number variation, and transcriptome sequencing (or other methods for quantitating RNA expression) may also be performed. The list of methods may be expanded to include novel methodology that may be developed during the course of this study or sample storage period.

Results from the genomic and transcriptional analyses will not be reported in the CSR.

10. SAFETY EVALUATION AND REPORTING

10.1. Recording and Reporting Adverse Events

10.1.1. General Guidelines

In this study, only targeted treatment-emergent AEs will be recorded:

- **All phases:** Treatment-emergent AESIs (grade ≥ 2 hypersensitivity and grade ≥ 2 IRRs; see Section 10.1.3)
- **All phases, including long COVID sub-study:** Treatment-emergent SAEs
- **Phase 1 only:** TEAEs (grade 3 or grade 4 only)
- **Long COVID sub-study only:** positive SARS-CoV-2 local test result, from the day of consent to sub-study until day 180
- **Long COVID sub-study only:** Any new medical condition that was diagnosed after randomization, until day 180

The investigator must promptly record treatment-emergent SAEs, treatment-emergent AESIs, and (in phase 1 only) grade 3 or 4 TEAEs occurring during the observation period (see Section 11.4.10.1). Medical conditions that existed or were diagnosed prior to the signing of the informed consent will be recorded as part of medical history. Abnormal laboratory values and vital signs observed at the time of informed consent should also be recorded as medical history. Any subsequent worsening (ie, any clinically significant change in frequency and/or intensity) of a pre-existing condition that is temporally associated with the use of the study drug should also be recorded as TEAE, provided that it fulfills the above criteria.

Throughout the study, the investigator will determine whether any treatment-emergent SAEs, treatment-emergent AESIs, and (in phase 1 only) grade 3 or 4 TEAEs have occurred by evaluating the patient. These events may be directly observed, reported spontaneously by the patient, or by questioning the patient at each study visit. Patients should be questioned in a general way, without asking about the occurrence of any specific symptoms. The investigator must assess all TEAEs to determine seriousness, severity, and causality, in accordance with the definitions in Section 10.2. The investigator's assessment must be clearly documented in the site's source documentation with the investigator's signature. The investigator should follow up on TEAEs (grade 3 or 4), treatment-

emergent SAEs, and treatment-emergent AESIs until they have resolved or are considered clinically stable.

Always report the diagnosis as the AE term. When a diagnosis is unavailable, report the primary sign or symptom as the AE term with additional details included in the narrative until the diagnosis becomes available. If the signs and symptoms are distinct and do not suggest a common diagnosis, report them as individual entries.

Laboratory results, vital signs, and other diagnostic results or findings should be appraised by the investigator to determine their clinical significance and whether they fulfil the criteria of TEAEs (grade 3 or 4), treatment-emergent SAEs, or treatment-emergent AESIs and will need to be reported. Isolated abnormal laboratory results, vital sign findings, or other diagnostic findings (ie, not part of a reported diagnosis) should be reported as TEAEs if they fulfill reporting criteria for the study (ie, treatment-emergent SAE, treatment-emergent AESI, TEAE [grade 3 or 4]) or require corrective treatment.

For events that are serious due to hospitalization, the reason for hospitalization must be reported as the serious adverse event (diagnosis or symptom requiring hospitalization). A procedure is not an AE or SAE, but the reason for the procedure may be an AE or SAE. Pre-planned (prior to signing the informed consent form [ICF]) procedures, treatments requiring hospitalization for pre-existing conditions that do not worsen in severity, and admission for palliative or social care should not be reported as SAEs (see Section 10.2 for definitions).

For deaths, the underlying or immediate cause of death should always be reported as an SAE.

Any treatment-emergent SAE that may occur subsequent to the reporting period (end of study) that the investigator assesses as related to study drug should also be reported.

All treatment-emergent SAEs, treatment-emergent AESIs, and pregnancies are to be reported according to the procedures in Section 10.1.3.

Note that patient-reported outcome (PRO) data (eg, patient-reported questionnaires, surveys, and instruments) are generally not reportable as individual AEs. However, if the investigator is made aware of any AE that (in his or her judgement) is related to study drug, the AE will be reported and recorded as described in Section 10.1.2.

10.1.2. Reporting Procedure

All treatment-emergent SAEs, treatment-emergent AESIs, and (in phase 1 only) treatment-emergent grade 3 or 4 AEs must be reported with investigator's assessment of the event's seriousness, severity, and causality to the blinded study drug. A detailed narrative summarizing the course of the event, including its evaluation, treatment, and outcome should be provided on the AE eCRF. Specific or estimated dates of event onset, treatment, and resolution should be included, when available. Medical history, concomitant medications, relevant concomitant procedures, and laboratory data that are relevant to the event should also be summarized in the narrative. For fatal events, the narrative should state whether an autopsy was or will be performed and include the results if available. Information not available at the time of the initial report must be documented in a follow-up report. Source documents (including hospital or medical records, diagnostic reports, etc) will be summarized in the narrative on the AE eCRF and retained at the study center and available upon request.

Urgent safety queries must be followed up and addressed promptly. Follow-up information and response to non-urgent safety queries should be combined for reporting to provide the most complete data possible within each follow-up.

10.1.3. Events that Require Expedited Reporting to Sponsor

The following events also require reporting to the Sponsor (or designee) within 24 hours of learning of the event:

- **Treatment-emergent SAEs**
- **Treatment-emergent AESIs** (serious and nonserious), defined as:
 - Grade ≥ 2 infusion-related reactions
 - Grade ≥ 2 hypersensitivity reactions
- **Pregnancy:** Although pregnancy is not considered an AE, it is the responsibility of the investigator to report to the Sponsor (or designee), within 24 hours of identification, any pregnancy occurring in a female study patient or female partner of a male study patient for up to 6 months after the last dose of study drug. Any complication of pregnancy affecting a female study patient or female partner of a male study patient, and/or fetus and/or newborn that meets the SAE criteria must be reported as an SAE. Outcome for all pregnancies should be reported to the Sponsor.

10.1.4. Other Adverse Events of Special Interest That Do Not Require Expedited Reporting to Sponsor

The following is considered an AESI and will require additional data collection (Section 9.2.9.4). However, these AESIs do not require expedited reporting to the Sponsor:

- **Long COVID sub-study only:** positive SARS-CoV-2 local test result
- **Long COVID sub-study only:** any new medical condition that was diagnosed after randomization

10.2. Definitions

10.2.1. Adverse Event

An AE is any untoward medical occurrence in a patient administered a study drug which may or may not have a causal relationship with the study drug. Therefore, an AE is any unfavorable and unintended sign (including abnormal laboratory finding), symptom, or disease which is temporally associated with the use of a study drug, whether or not considered related to the study drug (ICH E2A Guideline. Clinical Safety Data Management: Definitions and Standards for Expedited Reporting, Oct 1994).

10.2.2. Serious Adverse Event

An SAE is any untoward medical occurrence that at any dose:

- Results in **death** – includes all deaths, even those that appear to be completely unrelated to study drug (eg, a car accident in which a patient is a passenger).

- Is **life-threatening** – in the view of the investigator, the patient is at immediate risk of death at the time of the event. This does not include an adverse event that had occurred in a more severe form, might have caused death.
- Requires in-patient **re-hospitalization** (readmission after discharge) or **prolongation of existing hospitalization**. In-patient hospitalization is defined as a hospital admission (any duration) or an emergency room visit for longer than 24 hours. Prolongation of existing hospitalization is defined as a hospital stay that is longer than was originally anticipated for the event or is prolonged due to the development of a new adverse event as determined by the investigator or treating physician.
- Results in persistent or significant **disability/incapacity** (substantial disruption of one's ability to conduct normal life functions).
- Is a **congenital anomaly/birth defect**
- Is an **important medical event** – Important medical events may not be immediately life-threatening or result in death or hospitalization, but may jeopardize the patient or may require intervention to prevent one of the other serious outcomes listed above (eg, intensive treatment in an emergency room or at home for allergic bronchospasm; blood dyscrasias or convulsions that do not result in hospitalization; or development of drug dependency or drug abuse).

Criteria for reporting SAEs must be followed for these events.

10.2.3. Adverse Events of Special Interest

An AESI (serious or non-serious) is one of scientific and medical interest specific to the Sponsor's product or program, for which ongoing monitoring and rapid communication by the investigator to the Sponsor can be appropriate. Such an event might warrant further investigation in order to characterize and understand it.

Adverse events of special interest for this study are defined in Section [10.1.3](#).

10.2.3.1. Infusion-Related Reactions and Hypersensitivity

Infusion-related reactions are defined as any relevant adverse events that occurs during the infusion or up to day 4.

Hypersensitivity reactions are defined as any relevant adverse event that occurs during the infusion or up to study day 29.

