10. Patients discharged from the hospital will have weekly follow-up for treatment-emergent SAEs, treatment-emergent AESIs, and/or targeted concomitant medications as indicated in [Table 2](#) (post-discharge phone follow-up), which may occur as a phone call or an in-person visit. These visits may occur in addition to any in-person visit for sample collection listed for the given day. Phone visits will have a window of ± 1 day.
11. Medications will be reviewed and recorded. Only the targeted medications listed in Section [9.2.3.3](#) will be recorded in the eCRF.
12. Hematology, blood chemistry, and coagulation tests will be collected at the visits indicated and results will be entered in the eCRF. Note that coagulation tests will **not** be collected as part of the long COVID sub-study. Hematology, blood chemistry, and coagulation tests must be collected prior to dosing. Testing will be performed locally, and standard-of-care labs are acceptable.
13. Actual dosing time and PK sample collection times will be recorded.

14. At the baseline visit, blood samples for PK assessment will be taken predose and within 60 minutes after the end of infusion (EOI). The EOI sample should be collected from the arm contralateral to that used for IV infusion. If not medically feasible, the EOI sample can be drawn from the same arm, but not from the infusion catheter.

15. The window for predose ADA sample collection is as close to administration of study drug as is reasonable. Actual dosing times and ADA sample collection times will be recorded.

16. For patients who are not enrolled in the long COVID sub-study, day 57 will be the EOS per [Table 2](#). Patients enrolled in the long COVID sub-study will follow [Table 2](#) from screening to day 57, and [Table 3](#) from day 58 to their EOS on day 180.

For patients who consent to the long COVID sub-study after day 120, the day 120 sample collections may be performed outside of the specified visit window. Efforts should be made to collect these samples for all consenting patients.

17. On visit days when other assessments or sample collections are required, the site will verify that questionnaires have been completed prior to all other assessments or collections. The order of questionnaire completion is as follows: SE-LC19, PGIS, return to usual health, return to usual activities, SF-36, WPAI+CIQ, EQ-5D-5L.

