5.9. Analysis of Immunogenicity Data

5.9.1. Analysis of ADA Data

Immunogenicity variables will be summarized using descriptive statistics.

Immunogenicity will be characterized by the ADA responses and titers observed in subjects in the ADA analysis set. ADA response categories and titer categories are defined as follows:

ADA response categories:

- ADA Negative, defined as ADA negative response in the ADA assay at all time points, regardless of any missing samples.
- Pre-existing immunoreactivity, defined as either an ADA positive response in the ADA assay at baseline with all post first dose ADA results negative, OR a positive response

at baseline with all post first dose ADA responses less than 9-fold over baseline titer levels.

- Treatment-emergent response, defined as an ADA positive response in the ADA assay post first dose when baseline results are negative or missing. The treatment-emergent responses will be further characterized as Persistent, Indeterminate or Transient.
 - Persistent Response (only applicable to phase 1) – Treatment-emergent ADA positive response with two or more consecutive ADA positive sampling time points, separated by at least 16-week period (based on nominal sampling time), with no ADA negative samples in between, regardless of any missing samples.
 - Indeterminate Response –Treatment-emergent ADA positive response with only the last collected sample positive in the ADA assay, regardless of any missing samples.
 - Transient Response –Treatment-emergent ADA positive response that is not considered persistent or indeterminate, regardless of any missing samples.
- Treatment-boosted response, defined as a positive response in the ADA assay post first dose that is greater than or equal to 9-fold over baseline titer levels, when baseline results are positive.

Titer categories (Maximum titer values)

- Low (titer <1,000)
- Moderate (1,000 ≤ titer ≤ 10,000)
- High (titer >10,000)

The following analysis will be provided:

- Number (n) and percent (%) of ADA-negative subjects (pre-existing immunoreactivity or negative in the ADA assays at all time points) by treatment arms
- Number (n) and percent (%) of treatment-emergent ADA positive subjects by treatment arms and ADA titer categories
 - Number (n) and percent (%) of persistent treatment-emergent ADA positive subjects
 - Number (n) and percent (%) of indeterminate treatment-emergent ADA positive subjects

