5.10.2. Immunogenicity and Safety and Efficacy

Potential association between immunogenicity variables and safety may be explored with a primary focus on the following safety events during the TEAE period:

- Infusion reactions
- Hypersensitivity (SMQ: Hypersensitivity [Narrow])
- Anaphylaxis (SMQ: Anaphylaxis [Narrow])

Potential association between immunogenicity variables and efficacy endpoints may be explored (e.g. scatter plot or spaghetti plot).

The safety and efficacy analyses mentioned above will be conducted using the following categories:

- ADA positive subjects: Subjects with treatment-emergent or treatment-boosted response.
- Maximum post-baseline titer.
- NAb positive

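### SAP 5.10.2 groups patients by post-dose ADA status to examine infusion reactions that close at day 4, and has no category for the pre-dose ADA result

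*Protocol*

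**What the plan says.** Protocol 10.2.3.1 sets the two reaction windows: "Infusion-related reactions are defined as any relevant adverse events that occurs during the infusion or up to day 4", and "Hypersensitivity reactions are defined as any relevant adverse event that occurs during the infusion or up to study day 29". SAP 4.6.1 repeats both. Each patient receives one dose (Protocol 8.4).

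SAP 5.10.2 introduces the safety analysis as optional: "Potential association between immunogenicity variables and safety may be explored with a primary focus on the following safety events during the TEAE period". The events are infusion reactions, hypersensitivity and anaphylaxis. The efficacy counterpart is also optional and graphical: "Potential association between immunogenicity variables and efficacy endpoints may be explored (e.g. scatter plot or spaghetti plot". The grouping is then stated without that freedom: "The safety and efficacy analyses mentioned above will be conducted using the following categories". The first category is "ADA positive subjects: Subjects with treatment-emergent or treatment-boosted response". The others are maximum post-baseline titer and NAb positive.

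SAP 5.9.1 defines the ADA response classes. Its incidence summary has one line for "ADA-negative subjects (pre-existing immunoreactivity or negative in the ADA assays at all time points".

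A baseline ADA sample is taken. In the schedule footnotes for both phase 1 and phases 2/3: "The window for predose ADA sample collection is as close to administration of study drug as is reasonable".

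**The concern.** The natural question about a reaction to a first and only infusion is whether the patient already carried antibody when the infusion began. Section 5.10.2 does not ask it. It sorts patients by what their blood showed afterwards. It also leaves outside the ADA-positive group those patients who carried antibody into the infusion and showed no 9-fold rise.

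Protocol 3.3.2 names hypersensitivity, including infusion-related reactions, as an important identified risk. It names the clinical consequences of immunogenicity as an important potential risk, and gives that as the reason for collecting the samples. SAP 5.10.2 is where the two are brought together. If it is run as written and shows nothing, a reader could take reassurance that the display cannot give.

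**Working it through.** No sample size, power or alpha figure in the plan depends on this point, so there is no stated figure to reproduce. The check is of definitions and timing.

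**1. Order of grouping and outcome for infusion reactions**

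- Outcome: from the infusion to day 4 (Protocol 10.2.3.1, SAP 4.6.1).
- Treatment-emergent ADA needs a positive post-dose sample. Boosted ADA needs a post-dose titer at least 9-fold over baseline (SAP 5.9.1). Maximum titer is post-baseline by name. ADA-positive patients enter the NAb analysis set on a post-dose NAb result (SAP 3.4).
- A reaction during the infusion precedes every post-dose sample. A reaction up to day 4 precedes any sample taken later than day 4.
- A discharge sample may fall before or after day 4. If the late phase 2/3 sample is at about day 29 (an assumption; that row of the schedule could not be read reliably), it comes 29 − 4 = 25 days after the window closes. The argument needs only that the later samples fall after day 4.

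**2. Where baseline-positive patients go**

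| Baseline ADA | Post-dose ADA | Class in 5.9.1 | ADA positive in 5.10.2? |
|---|---|---|---|
| Negative | All negative | ADA negative | No |
| Negative or missing | Any positive | Treatment-emergent | Yes |
| Positive | All negative, or all below 9-fold | Pre-existing immunoreactivity | No; counted with ADA-negatives in the 5.9.1 summary |
| Positive | At least 9-fold over baseline | Treatment-boosted | Yes |

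The contrast that precedes the infusion is rows 3 and 4 against the baseline-negative patients. Section 5.10.2 instead sets apart rows 2 and 4.

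**3. What this can do to a real link (illustration only)**

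The documents give no ADA or reaction rates, and 5.10.2 plans no risk ratio and names no comparator. Everything here is assumed, including that ADA-positive patients are compared with everyone else. Let e be the treatment-emergent share, b the baseline-positive share, f the fraction of those boosted, and r0 and r1 the reaction risks without and with baseline ADA.

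- ADA-positive risk = (e·r0 + f·b·r1) / (e + f·b)
- Risk in the rest = [(1 − e − b)·r0 + (1 − f)·b·r1] / (1 − e − f·b)

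Take e = 5%, b = 3%, r0 = 1%, r1 = 10%, so that the ratio by pre-dose status is 10.

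- f = 0: 1.00% against (0.92 × 1% + 0.03 × 10%) / 0.95 = 1.28%; ratio 0.78.
- f = 30%: (0.05 × 1% + 0.009 × 10%) / 0.059 = 2.37% against (0.92 × 1% + 0.021 × 10%) / 0.941 = 1.20%; ratio 1.98.

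With b from 1% to 5% and r1 from 5% to 10%, the ratio by pre-dose status is 5 to 10. The post-dose grouping gives 0.68 to 0.96 when none are boosted and 1.2 to 2.3 when 30% are. The direction is dilution. The amount depends on inputs that the documents do not supply.

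**The case against.** The strongest reply is that this is a wording improvement to an optional, descriptive look. No test, estimate or endpoint is attached to it, and pre-existing immunoreactivity is not hidden: it is its own response class in SAP 5.9.1, with all titers listed. This largely stands, and it limits the weight of the point. It does not remove the point, because the SAP leaves open whether the analysis is run but fixes the categories if it is.

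A reader might infer more than the documents support:

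- **That the whole of 5.10.2 runs backwards in time.** This fits infusion reactions only. Hypersensitivity AESIs run to day 29, and the hypersensitivity and anaphylaxis searches cover the TEAE period, so events may come before or after a sample. For these, and for efficacy, the order is unspecified rather than reversed.
- **That all baseline-positive patients are treated as ADA-negative.** Boosted patients count as positive. The merger with ADA-negatives is in the 5.9.1 summary; 5.10.2 names no ADA-negative comparator.
- **That treatment-emergent ADA will look protective against death or ventilation to day 29, because patients must survive to be sampled.** Section 5.10.2 names no efficacy endpoint, day or risk comparison. Patients without a post-dose result leave the ADA analysis set (SAP 3.4) rather than being counted as negative. That selection would matter for any ADA-by-survival plot, but its size would rest on invented rates and an uncertain sampling day. Phase 1 also has ADA samples after day 29.

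**Conclusion.** The point holds in a narrow form. For infusion reactions, the categories in SAP 5.10.2 are normally measured after the outcome, and the one ADA status that precedes the infusion is collected but not used. Baseline-positive patients without a 9-fold rise fall outside the ADA-positive group, so an association between pre-existing ADA and infusion reactions could be diluted or missed.

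The size cannot be derived from the documents; the ratios above show direction under assumed rates and are not estimates. The finding rests on the stated definitions, on single dosing and on the day-4 window, and not on the exact day of the late phase 2/3 sample. No primary or secondary efficacy conclusion and no alpha is affected. What is at risk is a misleading safety display on a risk that the protocol itself names.

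**What to change.** In SAP 5.10.2:

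1. Add pre-dose ADA status, positive versus negative, as a category for infusion reactions, anaphylaxis and hypersensitivity. Pre-dose positive takes in both the pre-existing and the boosted patients. Show missing pre-dose results separately, since 5.9.1 places a post-dose positive with a missing baseline under treatment-emergent.
2. Show pre-existing immunoreactivity as its own row, not merged with ADA-negative.
3. Keep the post-dose ADA, titer and NAb categories as secondary displays that show event onset relative to the first positive sample.

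Two stricter rules are not recommended. Counting only events after the first positive sample would all but empty the infusion-reaction comparison. Restricting the efficacy look to baseline ADA would drop antibody that develops after dosing, which is part of the risk described in Protocol 3.3.2.

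The cost is SAP wording and one re-specified table. The pre-dose samples are already in the schedule. The drawback is that the baseline-positive group may be small, so its row may be too sparse to interpret.
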